9.4 Safety Analysis

The primary objective is the safety and tolerability of brexanolone, as evaluated by TEAEs. Other safety endpoints include clinical laboratory tests, vital signs, ECGs and concomitant medication usage. [REDACTED]

Safety data will be listed by subject and summarized descriptively by treatment group. All safety analyses will be performed on the Safety Set.

The safety endpoints and variables considered in the summary tables for this study are summarized in [Table 10](#).

Table 10: Safety Endpoints and Variables in the Summary Tables and Listings

Safety Evaluation	Incidence	Actual Value	Change from Baseline	Abnormality/Clinical Significance (CS)
AEs	X	*		
Concomitant Medications	X	*		
Laboratory assessments		X	X	*
ECG		X	X	*
Vital Signs		X	X	*

X = Safety Assessment will be summarized in tables

* = Safety Assessment will be presented in individual subject data listings

Abbreviations: AE=Adverse Event; ECG=electrocardiogram; [REDACTED]

9.4.1 Visit Windows

The mapping rule of unscheduled or early termination (ET) visit and the rule of flagging “analyzed record” are the same as described in [Section 9.3.3](#).

[Table 11](#) displays the visit windows for analysis of clinical laboratory parameters (including hematology, serum chemistry) parameters; [Table 12](#) displays the visit windows for analysis of 12-lead ECG; [Table 13](#) displays the visit windows for analysis of vital signs parameters; and [Table 14](#) displays the visit windows for analysis of [REDACTED].

Table 11: Visit Windows for Analysis of Clinical Laboratory Parameters

Scheduled Visit	Study Day/Hour of Expected Visit	Study Day/Hour Window for Visit
Baseline	D -1	D -7 to D1H0
D3H72	D3H72	>D1H0, \leq D3H72
D14	D14	>D4H0, \leq D33

Note: D = Day, H = Hour.

Statistical Analysis Plan (Methods)
Study 547-PPD-304Sage Therapeutics, Inc.
CONFIDENTIAL**Table 12: Visit Windows for Analysis of 12-lead Electrocardiogram Parameters**

Scheduled Visit	Study Day/Hour of Expected Visit	Study Day/Hour Window for Visit
Screening	D-1	D-7 to D-1
Baseline	D1H0	D1H0
D3H72	D3H72	>D1H0, \leq D3H72
D14	D14	>D4H0, \leq D33

Note: D = Day, H = Hour.

Table 13: Visit Windows for Analysis of Vital Signs Parameters

Scheduled Visit	Study Day/Hour of Expected Visit	Study Day/Hour Window for Visit
Screening	D -1	D -7 to D-1
Baseline	D1H0	D1H0
D1H2	D1H2	>D1H0, \leq D1H3
D1H4	D1H4	>D1H3, \leq D1H6
D1H8	D1H8	>D1H6, \leq D1H10
D1H12	D1H12	>D1H10, \leq D1H18
D1H24	D1H24	>D1H18, \leq D2H27
D2H30	D2H30	>D2H27, \leq D2H33
D2H36	D2H36	>D2H33, \leq D2H42
D2H48	D2H48	>D2H42, \leq D3H51
D3H54	D2H54	>D3H51, \leq D3H57
D3H60	D3H60	>D3H57, \leq D3H66
D3H72	D3H72	>D3H66, \leq D3H72
D7	D7	>D4H0, \leq D10
D14	D14	>D10, \leq D33

Note: D = Day, H = Hour.

Statistical Analysis Plan (Methods)
Study 547-PPD-304Sage Therapeutics, Inc.
CONFIDENTIAL

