6 STUDY DESIGN

6.1 Overall Design

In previous Versions 1 through 3 of this protocol, subjects were randomly assigned to active or placebo study drug in a blinded manner. With the current Amendment 3/Version 4, the study has been converted to an open-label study where all subjects will receive brexanolone.

This is a Phase 3, open-label study designed to evaluate the safety, tolerability, and PK of brexanolone in adolescent female subjects diagnosed (by Structured Clinical Interview for DSM-5 Axis I Disorders [SCID-5]) with PPD. Subjects will be administered a single, 60-hour continuous IV infusion of brexanolone. Each subject's involvement is up to 47 days, including a maximum 14-day Screening Period (from Day -14 through day -1, inclusive), a 3-day (60 hours of treatment and an additional 12 hours for completion of 72-hour assessments), and a Follow-up Period through Day 30 (\pm 3 days).

In Study 547-PPD-304, once subjects are confirmed as eligible for the study, subjects will be administered brexanolone. On the morning of dosing (Day 1), subjects will begin a 4-hour dose titration period of 30 mcg/kg/hour (0-4 hours), then 60 mcg/kg/hour (4-24 hours), then

Statistical Analysis Plan (Methods)
Study 547-PPD-304

Sage Therapeutics, Inc.
CONFIDENTIAL

90 mcg/kg/hour (24-52 hours); followed by a decrease to 60 mcg/kg/hour (52-56 hours), and 30 mcg/kg/hour (56-60 hours) as shown in [Table 1](#).

Table 1: Infusion Rates for 547-PPD-304

Time point	Infusion Rate (mcg/kg/hour)				
	Day 1 0-4 hours	Day 1 4-24 hours	Day 2-3 24-52 hours	Day 3 52-56 hours	Day 3 56-60 hours
Dose(mcg)	30	60	90	60	30

Total brexanolone dosing will occur over 60 hours.

The end of the Treatment Period coincides with the beginning of the Follow-up Period. Follow-up visits will be conducted on Day 7, Day 14, Day 21, Day 30.

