9.1.1 Study Day Definition

Study day is defined as follows:

- The day when the study drug infusion is started is designated as Day 1.
- For visit days after Day 1, study day = visit date – Day 1 date + 1.
- For visit days prior to Day 1, study day = visit date – Day 1 date. Thus, study days for the screening visit are negative numbers. There is no “Day 0”.

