9.3.3 Visit Windows

The unscheduled or early termination (ET) visit will be mapped to a scheduled visit for analysis using the date/time of collection/assessment as a basis to determine study day/hour and then study day/hour will be mapped to the intended visit. Once analysis visit windows get assigned, all visits, including scheduled visits, unscheduled visits, and ET visits will be eligible for being flagged as the “analyzed record” within the analysis window. A subject’s individual analysis visit window could potentially contain more than 1 visit. In the event of multiple visits falling within an analysis window or in case of a tie, the following rules will be used in sequence to determine the “analyzed record” for the analysis visit window:

- If there is a scheduled visit/day for the analysis visit window, then the scheduled visit/day data will be used.
- If there is no scheduled visit/day for the analysis visit window, the data closest to the scheduled study day/hour will be used.
- If there is no scheduled visit/day for the analysis visit window and there are visits equally close to the day/hour of scheduled visit, the latest data will be used.

[figure not shown]
The data not flagged as the “analyzed record” will also be listed in subject listings.

The Follow-up Period in this version of the protocol was reduced from Day 90 ± 7 days to Day 30 ± 3 days for consistency with the Follow-up Period in the adult PPD studies for brexanolone.

Statistical Analysis Plan (Methods)
Study 547-PPD-304

Sage Therapeutics, Inc.
CONFIDENTIAL

Tables 4 – 8 summarize the visit window for all the efficacy endpoint under both follow up schedules.

[figure not shown]
Statistical Analysis Plan (Methods)
Study 547-PPD-304

Sage Therapeutics, Inc.
CONFIDENTIAL

Statistical Analysis Plan (Methods)
Study 547-PPD-304

Sage Therapeutics, Inc.
CONFIDENTIAL

Statistical Analysis Plan (Methods)
Study 547-PPD-304

Sage Therapeutics, Inc.
CONFIDENTIAL

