12 APPENDICES

12.1 Appendix A: Schedule of Assessments

Statistical Analysis Plan (Methods)
Study 547-PPD-304

Sage Therapeutics, Inc.
CONFIDENTIAL

Study Procedure	Screening Period	Treatment Period/Inpatient Stay (Day 1 to Day 3)												Follow-up Period				
		D -14 to -1	D1	D1	D1	D1	D1	D1	D2	D2	D2	D3	D3	D3	D7 (±1d)	D14 and/or ET (±2d)	D21 (±3d)	D30 (±3d)
Visit Days	Hour	H0*	H2	H4	H8	H12	H24	H30	H36	H48	H54	H60	H72					
Informed consent process ^a	X																	
Inclusion/exclusion criteria	X	X																
Demographics	X																	
Medical history	X																	
Height	X																	
SCID-5	X																	
Physical examination ^b	X													X		X		
Body weight	X													X		X	X	
Clinical laboratory assessments ^c	X													X		X		
Drug and alcohol test ^d	X	X																
Pregnancy test ^e	X	X														X		X
Vital signs ^f	X	X ^g	X	X	X	X	X ^g	X ^g	X	X	X	X	X	X	X	X ^g		
12-lead ECG	X	X												X ^h		X		

Statistical Analysis Plan (Methods)
Study 547-PPD-304

Sage Therapeutics, Inc.
CONFIDENTIAL

Study Procedure	Screening Period	Treatment Period/Inpatient Stay (Day 1 to Day 3)												Follow-up Period			
		Visit Days	D -14 to -1	D1	D1	D1	D1	D1	D2	D2	D2	D3	D3	D7 (±1d)	D14 and/or ET (±2d)	D21 (±3d)	D30 (±3d)
Hour		H0 ^a	H2	H4	H8	H12	H24	H30	H36	H48	H54	H60	H72				
Plasma PK ^b			X		X	X	X	X	X	X	X		X	X			
Continuous pulse oximetry ^c								X									
Monitor for excessive sedation						X											
(Q2 hours during planned non-sleep periods)																	
Study drug infusion						X											
Adverse events								X									
Prior/concomitant medications ^d									X								
Nonpharmacological interventions ^e									X								

; D = day; ECG = electrocardiogram;

ET = early termination;

H = hour;

Scale; PK = pharmacokinetic; Q = every; SCID-5 = Structured Clinical Interview for Diagnostic and Statistical Manual of Mental Disorders, Fifth Edition.

* = All H0 procedures to be completed prior to dosing

a Depending on age at screening and local regulations, subjects will either sign an informed consent form, or will sign an adolescent assent form and their parent/guardian will sign a parental informed consent form.

b Full physical examination at screening. Symptom-directed physical examination may be conducted at subsequent time points.

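### SAP Tables 11–13 allow no time after Hour 72 in the Hour 72 window, so an unscheduled or ET record taken minutes later is mapped to Day 7 or Day 14

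*SAP*

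**What the plan says.** SAP Section 9.4.1 sets the analysis windows for laboratory tests (Table 11), ECG (Table 12) and vital signs (Table 13). In Table 13 the Hour 72 window is ">D3H66, \leq D3H72". In Tables 11 and 12 it runs from just after the start of infusion to the same upper limit. The next window opens after D4H0 in all three tables. It belongs to Day 7 for vital signs and to Day 14 for laboratory and ECG.

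Section 9.4.1 takes its mapping and selection rules from Section 9.3.3:

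- **Mapping:** "The unscheduled or early termination (ET) visit will be mapped to a scheduled visit for analysis using the date/time of collection/assessment".
- **Eligibility:** once windows are assigned, "all visits, including scheduled visits, unscheduled visits, and ET visits will be eligible for being flagged".
- **First selection rule:** "If there is a scheduled visit/day for the analysis visit window, then the scheduled visit/day data will be used".
- **Second selection rule:** "If there is no scheduled visit/day for the analysis visit window, the data closest to the scheduled study day/hour will be used".

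In the schedule of assessments (Appendix A), ET shares a column with Day 14; the column heading begins "D14 and/or ET (±2d".

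**The concern.** The Hour 72 window takes in time before its nominal hour and none after it. An unscheduled or ET record taken just after Hour 72 is clinically an Hour 72 observation, but the mapping rule sends it to a visit days later. The second selection rule favours the closest record, but it works only inside a window, after the boundary has already moved the record elsewhere.

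Mean change from baseline in laboratory measures, vital signs and ECG is a secondary endpoint (Section 5.2), summarised by scheduled time point. A displaced record can leave Hour 72 without a value, or put an end-of-treatment value under a follow-up visit. With 20 treated subjects planned (Section 6.2), one subject is 1/20 = 5% of a complete by-visit brexanolone summary.

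**Working it through.** **1. The pattern in Table 13.** Each limit is compared with the midpoint between the nominal hour and the next one.

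| Nominal hour | Next | Midpoint | Upper limit in Table 13 |
|---|---|---|---|
| 2 | 4 | 3 | 3 |
| 4 | 8 | 6 | 6 |
| 8 | 12 | 10 | 10 |
| 12 | 24 | 18 | 18 |
| 24 | 30 | 27 | 27 |
| 30 | 36 | 33 | 33 |
| 36 | 48 | 42 | 42 |
| 48 | 54 | 51 | 51 |
| 54 | 60 | 57 | 57 |
| 60 | 72 | 66 | 66 |
| 72 | 144 (Day 7) | 108 | 72 |

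All ten windows before Hour 72 close at the midpoint, 1 to 6 h after the nominal hour. Hour 72 closes 0 h after it. The Day 7 limit of Day 10 is also close to the midpoint between Days 7 and 14, which is (7 + 14)/2 = 10.5.

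Days 7 and 14 are taken here at the clock time of infusion start: (7 − 1) × 24 = Hour 144 and (14 − 1) × 24 = Hour 312.

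**2. Where a record just after Hour 72 goes.** Take an unscheduled or ET record at 72 h 10 min = 72.17 h. It lies past the Hour 72 limit and inside the next window.

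- Distance to Hour 72: 72.17 − 72 = 0.17 h.
- Distance to Day 7 (vital signs): 144 − 72.17 = 71.8 h.
- Distance to Day 14 (laboratory, ECG): 312 − 72.17 = 239.8 h.

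In Tables 11 and 12 the contrast is sharper. A record at Hour 1, which is 72 − 1 = 71 h early, counts as Hour 72, while one 10 minutes late counts as Day 14.

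**3. When a summary changes.** A scheduled record takes precedence within its window, which leaves four cases for a subject with such a record.

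| Scheduled Hour 72 | Scheduled Day 7 or Day 14 | Effect on by-visit summaries |
|---|---|---|
| Present | Present | None |
| Missing | Present | Hour 72 stays empty although a value 0.17 h away exists |
| Present | Missing | The later visit takes a value from about Hour 72 |
| Missing | Missing | Both of the above |

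TEAE summaries, the potentially clinically significant summaries that count any post-baseline occurrence, and the listings do not depend on these windows. The SAP gives no basis for estimating how many records are affected.

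**The case against.** The best defence is that Hour 72 is the plan's own period boundary. Section 6.1 describes 60 hours of treatment plus 12 hours to complete the 72-hour assessments, with follow-up starting where treatment ends. That may explain the limit. It does not make Day 14 a sensible place for an observation made minutes after Hour 72.

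For ET records the schedule gives partial support. Because ET shares the Day 14 column, assigning an ET laboratory or ECG record to Day 14 is consistent with Appendix A. This does not cover unscheduled records, or ET vital signs, which go to Day 7.

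A reader might infer two stronger points that the documents do not support.

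- **Late but compliant scheduled records drop out of Hour 72.** Appendix A permits Hour 72 laboratory tests and vital signs up to 30 minutes late and ECG up to 1 hour late. However, Section 9.3.3 states date/time mapping only for unscheduled and ET visits. The sentence that makes scheduled visits eligible concerns flagging after windows are assigned. The natural reading is that scheduled records keep their nominal visit, and the tolerances then have no bearing. The SAP does not say so outright, so a clarification is worthwhile.
- **D4H0 is midnight at the start of Day 4, so the windows overlap.** Section 9.1.1 does define study day by date ("For visit days after Day 1, study day = visit date" is the start of its formula). But the window tables label 24, 48 and 72 hours as D1H24, D2H48 and D3H72, which fits 24-hour blocks from the start of infusion and not calendar dates. On that scale D4H0 = 3 × 24 = Hour 72, and the windows meet without gap or overlap. D4H0 is mainly a notation slip, because it restarts an hour count that otherwise runs on from the start of infusion.

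**Conclusion.** The point holds in a limited form and is minor. The Hour 72 limit in Tables 11–13 allows no time after the nominal hour, departs from the midpoint pattern that Table 13 otherwise follows, and sends unscheduled or ET records taken minutes later to a visit about 72 or 240 hours away. That much follows directly from the stated limits and mapping rule. The distances assume that Days 7 and 14 fall at the clock time of infusion start.

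The effect is confined to descriptive by-visit summaries, and there only to subjects who have such a record and also lack the scheduled Hour 72 record or the scheduled Day 7 or Day 14 record. The primary safety endpoint is not touched.

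**What to change.** In each of Tables 11–13, replace the Hour 72 upper limit (D3H72) and the next window's lower limit (D4H0) with one common elapsed hour from the start of infusion that lies clearly after Hour 72.

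- **Vital signs:** Hour 108, from (72 + 144)/2, following the table's own pattern.
- **Laboratory and ECG:** the midpoint to Day 14, (72 + 312)/2 = Hour 192, or another stated hour clearly past Hour 72. With any such limit, state whether an ET record before it follows the window or the Day 14/ET column of Appendix A.

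Moving the limit only to the end of the longest collection tolerance (Hour 73) would not be enough. An unscheduled record at 73 h 10 min, 1.17 h from Hour 72, would still go to Day 7 or Day 14.

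As a clarification, add one sentence to Section 9.3.3: scheduled assessments keep their nominal visit, and only unscheduled and ET records are placed by date and time.

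The cost is SAP wording only: two limits in each of three tables, the sentence in Section 9.3.3 and the statement on ET records. Data collection and study conduct do not change.

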9.4.2 Adverse Events

The analysis of AEs will be based on the concept of TEAEs. A TEAE is defined as an AE with onset on or after the start of study drug infusion, or any worsening of a pre-existing medical condition/AE with onset on or after the start of study drug infusion.

All adverse events will be coded using MedDRA version 23.0 or higher and summarized by SOC and PT. Multiple occurrences of an AE are counted only once per subject per SOC and per PT for summary tables. Incidences will be presented in order of decreasing frequency of the brexanolone group by SOC and PT. Incidences will also be presented in order of decreasing frequency of the brexanolone group by PT only. In addition, summaries will be provided by severity (mild, moderate, severe) and by causality (related, not related) to study drug (see protocol section 12.2.2 for definitions). TEAEs leading to treatment discontinuation and study discontinuation and Serious AEs (SAEs) (see protocol section 12.2.1.2 for definition) with onset after the start of randomized infusion will also be summarized.

Summary tables of TEAEs will be presented by treatment and will summarize the number and percentage of subjects for the following:

- Any TEAE
- TEAEs by maximum severity to study drug (mild, moderate, severe)
- Treatment-emergent serious AEs (SAEs)
- TEAEs leading to discontinuation of study drug
- TEAEs leading to withdrawal from study
- AEs of special interest (AESIs), which include:
 - Excessive sedation
 - Loss of consciousness
 - Any sedation-related AE that leads to dose reduction, interruption, or termination

Subjects will be counted only once within each SOC and PT at the maximum severity in the following order: severe, moderate, and mild. An AE with missing severity will be considered as a severe AE. The incidences will be presented by descending frequency of SOC and then, within a SOC, by descending frequency of PT based on the subject count, and in alphabetical order of PT if the incidence within a PT is a tie.

Subjects will be counted only once within each SOC and PT at the strongest relationship to study drug in the following order: related, not related to study drug. If the relationship between the AE and the study drug is determined to be “possible” or “probable”, the event will be considered as related to the study drug. An AE with missing relationship to study drug will be considered as related to study drug.

A summary of most frequent TEAE just by preferred term where the incidence is more than 5% in any treatment group will be provided, sorted by decreasing overall frequency.

Statistical Analysis Plan (Methods)
Study 547-PPD-304

Sage Therapeutics, Inc.
CONFIDENTIAL

All AEs, SAEs (including those with onset or worsening before the start of randomized infusion), AEs leading to study drug discontinuation and AEs leading to death through the Day 30 Follow-up Visit (± 3 days), and all AESIs will be listed.

9.4.3 Prior and Concomitant Medications

Medications will be recorded at each study visit during the study and will be coded using World Health Organization-Drug dictionary enhanced (WHO-DDE) dated March 2018, or later.

Medications will be presented according to whether they are being taken prior to and/or during the study (concomitant):

- Prior medications are defined as all medications taken prior to the infusion of study treatment.
- Concomitant medications are defined as all medications taken on or after the infusion of study treatment starts through the Day 30 (± 3 days) visit. If medication dates are incomplete and it is not clear whether the medication was concomitant, it will be assumed to be concomitant.

Note that medication that started prior to the infusion of study drug and continued after the start of infusion will be summarized as prior medication and separately as concomitant medication. Details of prior and concomitant medications will be listed by subject, start date, and verbatim term.

Medication summaries will be performed by ATC level 2 term and PT separately for “Prior” or “Concomitant” medications as defined above based on the Safety Set.

Nonpharmacological interventions for PPD will be listed and summarized.

9.4.4 Clinical Laboratory

9.4.4.1 Hematology, Serum Chemistry, Coagulation

Blood samples will be collected for coagulation at screening, and hematology and serum chemistry, throughout the study. Analytes to be evaluated are summarized in [Table 15](#).

All blood samples will be sent to the central laboratory. Subjects may be considered eligible for the study based on results reported by a local laboratory; however, screening samples must also be sent to the central laboratory. Both local and central screening laboratories must adhere to the visit window provided in [Appendix A](#).

Table 15: Summary of Laboratory Analytes

Hematology	Complete blood count (red blood cells, white blood cells with differentiation and absolute values, hemoglobin, hematocrit, reticulocytes, and platelets)
------------	--

Statistical Analysis Plan (Methods)
Study 547-PPD-304Sage Therapeutics, Inc.
CONFIDENTIAL

Coagulation (at Screening only)	Activated partial thromboplastin time, prothrombin time, and international normalized ratio
Biochemistry	Serum electrolytes (sodium, potassium, chloride, bicarbonate or total carbon dioxide, calcium, and phosphorus) renal function tests (creatinine and blood urea nitrogen); liver function tests (total bilirubin, alkaline phosphatase, aspartate aminotransferase, alanine aminotransferase, and gamma glutamyl transferase); thyroid stimulating hormone; total protein; albumin and glucose (fasting or non-fasting)

All clinical laboratory test results outside the reference range will be interpreted by the Investigator as abnormal, not clinically significant; or abnormal, clinically significant (CS). Screening results considered abnormal and CS at the Screening Visit may make the subject ineligible for the study pending review by the Investigator or Medical Monitor. Clinically significant abnormal results after screening will be considered and reported as AEs.

Summary tables will include descriptive statistics for the actual values and changes from baseline by scheduled time point in hematology, serum chemistry, and coagulation by treatment group. Frequency counts and percentages will be presented over time for these categorical data by treatment.

Shift analysis pre- and post-treatment will be presented for the following laboratory categories (low, normal and high).

Number and percent of subjects with liver injury as defined by Hy's law will be presented. Hy's law is defined as ALT or AST > 3 times of upper limit of normal; and total bilirubin > 2 times of upper limit of normal, and alkaline phosphatase < 2 time of upper limit of normal.

All parameters will be converted to consistent units according to the International System of Units (SI) before summarization.

All clinical laboratory results will be listed by subject and timing of collection. Out-of-range values will be flagged as low, high, or abnormal, where applicable.

The number and percentage of subjects with potentially clinically significant (PCS) values at any time after study drug infusion will be summarized by treatment group for the hematology and chemistry parameters defined in [Table 16](#) and [Table 17](#). PCS laboratory values will also be listed by subject.

Statistical Analysis Plan (Methods)
Study 547-PPD-304Sage Therapeutics, Inc.
CONFIDENTIAL**Table 16: Hematology Potentially Clinically Significant Values**

Laboratory Parameter	Sex	Units	Criteria for PCS Values (Observed values)	
			High	Low
Hemoglobin	Male	g/L	>185	<115
	Female	g/L	>170	<100
Hematocrit	Male	Fraction of 1	>0.55	<0.385
	Female	Fraction of 1	>0.49	<0.345
Platelet count		10 ⁹ /L	>600	<125
White blood cell		10 ⁹ /L	>15	<2.5
Basophils		10 ⁹ /L	>0.5	NA
Eosinophils		10 ⁹ /L	>1.5	NA
Neutrophils		10 ⁹ /L	NA	<1.5
Lymphocytes		10 ⁹ /L	>6.0	<0.5
Monocytes		10 ⁹ /L	>1.4	NA

Abbreviations: PCS = Potentially Clinically Significant

Statistical Analysis Plan (Methods)
Study 547-PPD-304Sage Therapeutics, Inc.
CONFIDENTIAL**Table 17: Chemistry Potentially Clinically Significant Values**

Laboratory Parameter	Units	Criteria for PCS Values (Observed values)	
		High	Low
Albumin	g/L	>70	<28
Blood urea nitrogen	mmol/L	>10.71	NA
Calcium	mmol/L	>2.75	<2.0
Chloride	mmol/L	>120	<90
Creatinine	mmol/L	>3xULN or >3x Baseline	
Gamma Glutamyl Transferase		>3xULN	
Glucose	mmol/L	>13.9	<2.8
Sodium	mmol/L	>150	<132
Potassium	mmol/L	>5.4	<3.3
Protein	g/L		<45
Bicarbonate	mmol/L	>34	<18
Chloride	mmol/L	>120	<90
Phosphorus	mmol/L	>1.94	<0.61
Liver Function Tests (LFT)			
Bilirubin	µmol/L	>2xULN	NA
Aspartate Aminotransferase	U/L	>3xULN	NA
Alanine Aminotransferase	U/L	>3xULN	NA
Alkaline Phosphatase	U/L	>1.5xULN	NA

Abbreviations: PCS = Potentially Clinically Significant

Liver function tests will be monitored closely for potentially clinically significant values, and will be summarized for occurrence any time post-baseline for the following parameters for these PCS threshold (for condition involving >1 parameter, the results need to be from the same timepoint):

Alanine Aminotransferase: >3xULN, >5xULN, >10xULN

Aspartate Aminotransferase: >3xULN, >5xULN, >10xULN

Alanine Aminotransferase or Aspartate Aminotransferase: >3xULN, >5xULN, >10xULN

Alkaline Phosphatase: >1.5xULN, >2xULN

Total Bilirubin: >1.5xULN, >2xULN

Total Bilirubin > 2xULN AND (Alanine Aminotransferase or Aspartate Aminotransferase >3xULN)

Statistical Analysis Plan (Methods)
Study 547-PPD-304

Sage Therapeutics, Inc.
CONFIDENTIAL

Total Bilirubin >2xULN AND Alkaline Phosphatase >2xULN AND (Alanine Aminotransferase or Aspartate Aminotransferase >3xULN)

Any lab results considered clinically significant by the investigator will be captured as AEs events, hence will show up in AE displays.

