6.2 Sample Size and Power

No formal sample size calculation was made for this study. The planned sample size of 20 adolescent subjects treated with brexanolone should be appropriate to characterize the PK and safety profile.

The planned sample size of 20 includes those subjects who received brexanolone as blinded study drug during earlier versions of the protocol when the study was a randomized, double-blind, placebo-controlled study.

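### Does the Hy's law count need its own rule that all results come from the same post-baseline timepoint?

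*SAP*

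**What the plan says.** SAP section 9.4.4.1 announces the output: "Number and percent of subjects with liver injury as defined by Hy's law will be presented". The definition that follows has three parts: ALT or AST above 3 times ULN, then "total bilirubin > 2 times of upper limit of normal, and alkaline phosphatase < 2 time of upper limit of normal". It says nothing about when the results must be obtained or whether they must come from one sample.

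The neighbouring counts do carry timing. For the hematology and chemistry parameters in Tables 16 and 17, potentially clinically significant "values at any time after study drug infusion will be summarized by treatment group". Later in the section, a list of liver test thresholds is summarised for occurrence after baseline, "for the following parameters for these PCS threshold (for condition involving >1 parameter, the results need to be from the same timepoint". Its two combined rows are bilirubin above 2 times ULN with ALT or AST above 3 times ULN, and "Total Bilirubin >2xULN AND Alkaline Phosphatase >2xULN AND (Alanine Aminotransferase or Aspartate Aminotransferase >3xULN". No row in the list has alkaline phosphatase (ALP) below 2 times ULN.

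The section also states: "All clinical laboratory results will be listed by subject and timing of collection".

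**The concern.** Hy's law is meant to pick out transaminase and bilirubin rises that occur together without a marked rise in ALP. A three-part definition without timing could be programmed as three separate questions, each answered yes if the criterion was met at any visit. A subject with raised ALT at 72 hours and raised bilirubin only at Day 14 would then be counted. So would a subject with all three tests raised at 72 hours whose ALP had fallen by Day 14, although no single draw met the definition.

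Two features of the text encourage the worry. The same-timepoint rule is worded for the list that follows it, and Hy's law is not in that list. The list's only three-part row also takes ALP in the opposite direction, with no explanation, which raises the question whether it was intended as the Hy's law row.

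Safety is the primary objective and liver injury is a named output. Tables that disagree, with a three-part count larger than the two-part row that should contain it, would be awkward to explain.

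**Working it through.** The plan gives no figure to reproduce. The check asks how far the two readings can differ, and then which reading the text supports.

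**Inputs**
- Two scheduled post-baseline laboratory timepoints, 72 hours and Day 14 (SAP section 9.4.1, "Table 11: Visit Windows for Analysis of Clinical Laboratory Parameters").
- Three yes/no criteria per draw: A = ALT or AST above 3 times ULN; B = bilirubin above 2 times ULN; L = ALP below 2 times ULN. Otherwise ALP is taken as above 2 times ULN.
- "The planned sample size of 20 adolescent subjects treated with brexanolone" (SAP section 6.2).

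**How far the readings differ**
1. Each draw has 2 × 2 × 2 = 8 patterns, so two draws have 8 × 8 = 64.
2. Each criterion met at some draw: 2² − 1 = 3 ways per criterion, 3 × 3 × 3 = 27 patterns.
3. All three met at one draw: 64 − 7² = 15 patterns.
4. Every pattern in step 3 is also in step 2, so none is missed and 27 − 15 = 12 are extra.
5. In 6 of the 12, A and B occur together only with raised ALP, and L holds at the other draw: 2 choices of draw × 3 states of A and B at the other draw.
6. In the other 6, A and B never occur together: 2 ways to place them × 3 ways for L to hold at least once.
7. If a pre-dose draw were also eligible: 7³ = 343 patterns against 512 − 343 = 169, a difference of 174.

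**What the planned same-timepoint rows already show**
1. Two-part row (A and B at one draw): 64 − 6² = 28 patterns.
2. Row with raised ALP (A and B at one draw, ALP above 2 times ULN): 64 − 7² = 15 patterns, all contained in the 28.
3. In the first row but not the second: 28 − 15 = 13 patterns, all of them Hy's law at a single draw.
4. The remaining 15 − 13 = 2 single-draw Hy's law patterns have A and B at both draws with ALP on either side of the threshold, so those subjects appear in both rows.

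The rows classed by ALP therefore identify 13 of the 15 simultaneous patterns, and the listing settles the other 2. An ALP of exactly 2.0 times ULN falls in neither three-part condition.

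**What the text supports**
- The definition joins three criteria and is silent on timing. It does not say that they may be met at any time or at different visits. The figure of 27 comes from supplying that reading.
- Table 15 places all the analytes together as liver function tests within the biochemistry panel, so evaluating the three criteria draw by draw is straightforward.
- The same section, on the same tests, says how a condition with more than one parameter is handled: post-baseline, one timepoint. Hy's law is such a condition.
- None of the rows in the list has a label. The raised-ALP row is not called Hy's law, and it works as the complement of the Hy's law ALP limit.

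**The case for a change.** The best case for a change is that the authors saw that combined liver conditions need a timing rule, wrote one, and by its grammar confined it to a list from which Hy's law is absent. A plan should not leave a named safety output to inference. One misclassified subject would be 1/20 = 5% of the planned brexanolone group, and a listing lets a reader find an error without making the table right. Unscheduled and early termination draws also enter the analysis windows, so more than two draws per subject are possible. The remedy would be a single phrase.

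Part of this stands: the Hy's law sentence does omit timing, and the rule's wording does not formally reach it. What does not stand is the step from silence to a wrong count. The cross-visit reading has no support in the text and departs from the convention that the section states for conditions of this type. The post-baseline half is weaker still. The section already makes clinically significant screening abnormalities a possible ground for ineligibility, and both neighbouring abnormality counts concern results after dosing. The suggestion that the raised-ALP row has the wrong sign rests on nothing beyond the lack of a label, which it shares with every other row.

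**Conclusion.** No change follows. This is missing detail that an analyst would fill correctly from the same section by requiring all Hy's law results to be post-baseline and from one timepoint. It is not a stated rule that gives a wrong answer.

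The 12 extra patterns out of 64 arise only under an any-visit reading that the plan does not state. They carry no weights, because the document gives no event rates. Even under that reading no simultaneous case is lost. The count is descriptive and no formal test depends on it. The planned two-part and raised-ALP rows expose most discrepancies, and the listing by subject and collection time resolves the rest. The conclusion assumes that the programmer applies the section's timing rule to all its multi-parameter liver conditions, and that such events are few enough to be checked individually, which is reasonable with 20 planned brexanolone subjects.
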